## Sensitivity analyses

1. Given the high variability in morning void spot urine UPCR values, the baseline will be defined as the average of the screening and Day 1 morning void spot urine UPCR values if both are available. The UPCR analyses will be repeated using this baseline definition. If only one of 2 morning void spot urine values is available, that value will be used as the baseline. Post-baseline assessments will use the same approach as for the primary analysis prioritizing morning void spot urine and replacing missing assessments with 24 hour urine results where available.
2. As 24-hour urine evaluations were not available for all subjects. The following analysis will be conducted:
  - Baseline will be calculated by averaging the screening and Day 1 values using 24 hour urine results where available.
  - Post baseline assessments will prioritize the 24 hour results where available. Spot urine values will be used when 24 hour assessments are not available.
3. A sensitivity analysis will be conducted using the same approach as the primary analysis, however, for subjects who have been identified as taking non-allowed medications, all data after the initiation of the non-allowed medication will be imputed using the last observation prior to the initiation of the non-allowed medication.

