9.4. Sample Size Justification

Assuming the standard deviation (SD) for the change from baseline in the logarithmic transformation of UPCR is 0.70, with 10 subjects per treatment group, the 90% confidence interval (CI) for the between group difference in the log scale will have a $\frac{1}{2}$ width of 0.543. In other words, if the ratio of the treatment over placebo is 0.5 (50% reduction from placebo) in UPCR, the 90% CI will be (0.29, 0.86) (i.e., 14% to 71% reduction).

Assuming SD =8.5 for change from baseline in eGFR, with 10 subjects per group, the 90% CI for the between group difference will have a $\frac{1}{2}$ width of 6.6. If the difference between treatment and placebo is observed to be 10 mL/min/1.73m², the 90% CI will be (3.4, 16.6).

Note the above calculation is based on the SD estimated from Study CL005_140 and an unadjusted 2-sided alpha of 10%.

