## 2.2 Study Design

### 2.2.1 Overview

This study will evaluate the efficacy, safety, tolerability, and pharmacokinetics of up to 12 weeks of treatment with each of three dose regimens of CCX140-B or placebo, when used in combination with stable standard of care therapy in subjects with FSGS with significant proteinuria, assessed as UPCR > 1g/g at Screening.

The target is to enroll 40 adult male or female subjects in this randomized, double-blind, placebo-controlled, Phase 2 study. Subjects will be randomized 1:1:1:1 to one of four treatment groups:

- Group A: Placebo (N=10)
- Group B: CCX140-B 5 mg once daily (N=10)
- Group C: CCX140-B 10 mg twice daily (N=10)
- Group D: CCX140-B 15 mg twice daily (N=10)

[figure not shown]
Subjects will be screened within a period not to exceed 28 days prior to Study Day 1 (the first day of dosing). All subjects will take blinded study medication in the morning and evening, with or without food, for 84 consecutive days. Following the 84-day blinded dosing period, all subjects will take open label CCX140-B for an additional 84 days at the highest dose under evaluation, currently planned to be 15 mg twice daily.

During the treatment period, eligible subjects will visit the study center on Study Days 1, 8, 15, 29 (Week 4), and Weeks 8, 12 (primary endpoint), 13, 16, 20, and 24 for study procedures including interval history, physical examination and vital signs, ECG, study questionnaires, and collection of blood and urine. Subjects will discontinue study drug as of Study Day 169 (Week 24) and will return for a follow up visit on Week 28. When feasible, upon discontinuation of treatment for any reason a sample of whole blood should be collected for assessment of elimination 2, 7 and 14 days after the final dose of CCX140-B (or placebo).

A study schema is depicted in Figure 1. All study procedures are presented in Table 1.

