### *2.2.4 Sample Size Determination*

Assuming the standard deviation (SD) for the group difference in change from baseline in the logarithmic transformation of UPCR is 0.70, with 10 subjects per treatment group, the 90% confidence interval (CI) for the between group difference in the log scale will have a  $\frac{1}{2}$  width of 0.543. In other words, if the ratio of the treatment over placebo is 0.5 (50% reduction from placebo) in UPCR, the 90% CI will be (0.29, 0.86) (i.e., 14% to 71% reduction).

Assuming SD = 8.5 for the group difference in change from baseline in eGFR, with 10 subjects per group, the 90% CI for the between group difference will have a  $\frac{1}{2}$  width of 6.6. If the difference between treatment and placebo is observed to be 10 mL/min/1.73m^2, the 90% CI will be (3.4, 16.6).

Note the above calculation is based on the SD estimated from Study CL005\_140 and an unadjusted 2-sided alpha of 10%.

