### 3.1.5 *Hypothesis Testing*

As this is an exploratory study in a rare disease, unless specified otherwise, all statistical tests and confidence intervals will be based on a 2-sided alpha of 0.10. No multiplicity adjustment will be applied to the multiple dose and multiple endpoints comparisons.

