### 3.4.1 Primary Efficacy Endpoint

#### UPCR Change from Baseline

The primary efficacy endpoint (UPCR) will be summarized by treatment group over time using descriptive statistics. Spaghetti plots of UPCR as well as percent change of UPCR (derived from morning void spot urine. If missing 24 hour urine evaluations will be used, if available) from baseline to weeks 4, 8, 12, 13, 16, 20, 24, and week 28 (if available) will be produced by treatment group and for all individual patients for visual inspection. Additionally, percent change of UPCR from week 12 to week 13, 16, 20, 24, and week 28 will be summarized by prior treatment group during the open-label period. The same analyses of for UPCR will be performed at baseline, week 12 and week 24 solely using UPCR values derived from 24-hour urine evaluations (missing assessments will not be replaced with morning void spot urine values).

The primary analysis will use the morning void spot urine results. If baseline or post-baseline morning void spot urine results are not available, 24 hour urine results will be used where available. Please note 24-hour urine assessments at Day 1, Week 12 and Week 24 were added after Protocol Amendment 4.0.

For inferential analysis of the ratio to baseline, UPCR will be loge-transformed to alleviate skewness of the data since data are not normally distributed. A mixed effect model for repeated measures (MMRM) will be performed in the ITT population with treatment, group, visit, and treatment-by-visit interaction as factors and baseline value and age as covariates. Least squares mean differences and the corresponding 90% confidence intervals (CI) between each of the CCX140-B (5, 10, or 15 mg) groups and the placebo group will be back transformed to the original scale. Corresponding P-values will also be presented.

In the MMRM model, missing data will not be imputed. This analysis is unbiased under the missing at random (MAR) assumption. Toeplitz covariance matrix will be used to model within-subject variance-covariance structure for the model errors. If the model does not converge using the Toeplitz covariance matrix, AR(1) covariance matrix will be used. If convergence is still not met, then compound symmetry (CS) will be used.

The code used to generate the MMRM analysis will be similar to the following:

```
*****
Note:
TRT01AN = randomized treatment group (numeric):
    1=Placebo, 2=CCX140-B 5 mg, 3=CCX140-B 10 mg, 3=CCX140-B 15 mg
VISITN = Visit Number

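### The primary UPCR model leaves out the screening UPCR, a second pre-randomisation measurement that could narrow the interval slightly; it could be added as a covariate with a missing-value rule

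*SAP*

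**What the plan says.** SAP 3.4.1 specifies a mixed model for repeated measures on the log ratio to baseline, with treatment, visit and "treatment-by-visit interaction as factors and baseline value and age as covariates". The code in that section agrees: log baseline and age are the only covariates. SAP 3.1.3 defines baseline as the last non-missing value before dosing, usually Day 1. SAP 3.4.1 takes it from the morning-void spot sample and uses a 24-hour result if the spot result is missing.

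The SAP's sensitivity analyses open with "Given the high variability in morning void spot urine UPCR values". Item 1 then repeats the UPCR analyses with the average of the screening and Day 1 spot values as baseline, or the single value if only one exists. Item 2 also averages screening and Day 1, giving preference to 24-hour results.

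The screening UPCR is a scheduled first morning void (Protocol 7.1 and Time and Events Table). It must be at least 1 g/g for entry (Protocol 5.2, criterion 2), and it sets the 3.5 g/g stratum at randomisation (Protocol Section 4). It does not appear in the primary model. The SAP's Covariates and Subgroups section says that efficacy analyses may be adjusted for a list of variables. That list has dichotomised baseline UPCR but no continuous screening value.

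**The concern.** If a single spot UPCR is as noisy as the SAP says, one such value is an imperfect measure of a subject's underlying proteinuria. Between-subject variation that a second measurement could explain then stays in the error term. The second measurement is already scheduled and is taken before randomisation.

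Precision is the main limit of this trial. Allocation is equal across four arms ("Subjects will be randomized 1:1:1:1 to one of four treatment groups"), with a target of 10 in each. The SAP's own illustration shows how wide the result will be: "if the ratio of the treatment over placebo is 0.5 (50% reduction from placebo) in UPCR, the 90% CI will be (0.29, 0.86"). What is at stake is interval width in the primary comparison. Bias is not at issue, because the estimate is valid with or without the extra covariate.

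**Working it through.** **1. The plan's own figure.** Inputs: two-sided 90% intervals ("all statistical tests and confidence intervals will be based on a 2-sided alpha of 0.10") and, from Protocol 9.4, "Assuming the standard deviation (SD) for the change from baseline in the logarithmic transformation of UPCR is 0.70, with 10 subjects per treatment group".

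- Half-width = t(0.95; 18 df) × 0.70 × √(2/10) = 0.543, as stated.
- At a ratio of 0.5 the interval is 0.5 × exp(±0.543) = 0.29 to 0.86, as stated.
- SAP 2.2.4 words the same input differently: "Assuming the standard deviation (SD) for the group difference in change from baseline in the logarithmic transformation of UPCR is 0.70". Only the per-subject reading gives 0.543. Taking 0.70 as the SD of the difference itself gives 1.214. The per-subject reading is used below.

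**2. Price of one more covariate.** A Week 12 ANCOVA on 40 complete subjects stands in for the MMRM contrast. With q covariates the error df are 36 − q, and expected chance imbalance multiplies the variance by 1 + q/(35 − q).

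- Day 1 and age (q = 2): 34 df, imbalance factor 1 + 2/33.
- With screening added (q = 3): 33 df, imbalance factor 1 + 3/32.
- Price = (1.6924/1.6909) × √[(1 + 3/32)/(1 + 2/33)] = 1.0008 × 1.0155 = 1.0164, that is 1.6% of the half-width.
- Break-even: 1 − 1/1.0164² = 3.2%. Screening must explain about 3% of the residual variance to pay for itself.

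**3. Gain under shared signal plus visit noise.** The documents give neither variance, so both are assumptions on the log scale: between-subject variance B from 0.25 to 0.80 and single-visit noise variance E from 0.06 to 0.245. With the SD of change fixed at 0.70:

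- Week 12 variance V = B + E + (0.49 − 2E)
- Residual variance, Day 1 only: V − B²/(B + E)
- Residual variance, Day 1 and screening: V − B²/(B + E/2)

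| B | E | Day 1 only | Day 1 + screening | Ratio | Half-width before price | Half-width net |
|---|---|---|---|---|---|---|
| 0.25 | 0.06 | 0.478 | 0.457 | 0.955 | −2.3% | −0.7% |
| 0.25 | 0.245 | 0.369 | 0.327 | 0.887 | −5.8% | −4.3% |
| 0.80 | 0.06 | 0.486 | 0.459 | 0.945 | −2.8% | −1.2% |
| 0.80 | 0.245 | 0.433 | 0.351 | 0.812 | −9.9% | −8.4% |

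Net change = √ratio × 1.0164 − 1. The value E = 0.245 is the ceiling, because 2 × 0.245 = 0.49 makes all of the change variance visit noise.

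**4. Effect of the entry threshold.** Requiring screening UPCR of at least 1 g/g restricts the range of the screening covariate and weakens it. In simulation with an assumed median of 3 g/g before selection, the net gain was about 0.7% to 7%. With an assumed median of 1.5 g/g the lower end fell to about 0.2%. Coverage of the 90% interval stayed close to nominal (about 88% to 91%) with and without the threshold. Taken together, the net gain is roughly 0.3% to 8%.

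**5. When it does not pay.** If the correlation between visits decays serially, so that screening tells nothing about Week 12 once Day 1 is known, the residual variance is unchanged and only the price remains. For a Day 1 to Week 12 correlation of 0.7, the half-width goes from 0.503 to 0.511 (+1.6%). In that scenario the interval was narrower in only 21% of simulated trials.

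**6. Against the SAP's averaged baseline.** With equal correlation between visits of 0.5, 0.7 and 0.9, simulation gave changes in half-width of −5.4%, −8.3% and −11.3% for the averaged baseline, and −4.3%, −7.3% and −10.5% for the added covariate. Equal correlation with this SD of change means that all change variance is visit noise, so these are best-case figures. Under serial decay at 0.7 the averaged baseline loses 4.9% and the added covariate 1.6%.

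**The case against.** The strongest case against has four parts.

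- **The SAP already acts on the noise.** Sensitivity analysis 1 uses the screening value, has its own rule for a missing value, and gains slightly more than the added covariate when correlations are equal. This stands as far as it goes, and nobody should infer that the SAP ignores the problem. But that analysis is secondary, it changes the endpoint by redefining baseline, and it loses more if correlations decay. It does nothing for the primary interval.
- **The size rests on assumptions.** This stands. The documents give no visit-noise variance and no correlation, and at low noise the gain is close to nothing.
- **Screening UPCR is selected by the entry threshold.** Selection precedes randomisation and acts on all arms alike, so validity is unaffected. It does reduce the gain, as step 4 shows.
- **A missing covariate would remove a subject from the model.** This stands. Protocol 7.1 lets earlier clinical-practice results serve for eligibility, and sensitivity analysis 1 foresees subjects with only one spot value. Losing one subject from a 10-against-10 comparison widens the interval by √[(1/10 + 1/9)/(2/10)] − 1 = 2.7%, more than the gain at low noise. A fallback rule is therefore part of the change.

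It is also fair that the study is exploratory, that no multiplicity adjustment applies, and that Protocol 9.3.5 says inferential analysis may not be appropriate.

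**Conclusion.** The point holds as a cheap improvement. The primary model uses one pre-dose UPCR and age. The SAP itself calls spot values highly variable, and the screening value enters the analysis of UPCR change only through sensitivity analyses. Adding it as a covariate is valid and leaves the endpoint unchanged. The expected net narrowing of the 90% interval is roughly 0.3% to 8% under the assumed variances, with near zero at low noise and typically mid single digits at higher noise. Against that stands a possible net loss of about 1.6% if screening adds nothing beyond Day 1. The SAP's own stated reason, noise in single spot values, makes a gain more likely than a loss but does not settle it.

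A reader might infer more than this, and three stronger readings are not supported:

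- That the adjustment is free. It costs about 1.6% of the half-width at N = 40.
- That every subject has a usable screening spot value. Protocol 7.1 and SAP sensitivity analysis 1 both leave room for its absence.
- That the planned primary analysis is wrong or biased. It is valid, and only its precision is in question.

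The figures come from a complete-data ANCOVA in place of the Toeplitz MMRM, and dropout is not modelled.

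**What to change.** Before unblinding, amend SAP 3.4.1 in three respects:

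1. Add log screening first-morning-void UPCR as a covariate in the primary MMRM, next to log baseline UPCR and age.
2. Keep the endpoint as change from Day 1 and keep the existing baseline definition.
3. State a fallback for a missing screening spot value, for example substituting the subject's log Day 1 UPCR, so that no subject leaves the model.

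Keep the averaged-baseline analysis as a sensitivity analysis, and report the model without the screening term next to the primary result so that the effect of the change can be seen. Record the change in SAP Section 6.

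The cost is one model term, one derivation rule and one error degree of freedom. No extra subject, visit or assay is needed.

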2.4.1. CCR2 Inhibitor CCX140-B: Clinical Experience

CCX140-B is an orally administered, selective small molecule inhibitor of the chemokine receptor known as CCR2. To date it has not been administered in subjects with biopsy-proven FSGS.

CCX140-B has been assessed in 4 Phase 1 clinical trials in healthy volunteers, one Phase 2 trial in subjects with diabetes, and two Phase 2 trials in subjects with diabetic nephropathy. A tabular summary of clinical studies conducted with CCX140-B and submitted to IND 114469 are provided in the Investigator's Brochure.

Efficacy findings in study CL005_140 in patients with diabetic nephropathy and proteinuria provide support for exploring CCX140-B in FSGS. In that trial, 192 subjects with diabetic nephropathy received uninterrupted dosing for up to 52 weeks with placebo, 5 mg daily of CCX140-B or 10 mg daily of CCX140-B. Compared to placebo, CCX140-B was associated with greater reduction in albuminuria. Specifically, changes from baseline in the ratio of urinary albumin to creatinine (UACR) averaged -2% in the placebo group (95% CI -11% to +9%), -18% in the CCX140-B 5 mg group (95% CI -26% to -8%), and -11% in the CCX140-B 10 mg group (95% CI -20% to -1%). The decrease in UACR was observed at the earliest measured time point (Day 15) and reached a maximum decrease by the Day 85 visit (de Zeeuw et al., 2015).

Of note, subjects entering the study were stratified based on the level of proteinuria at baseline. In a pre-specified subset analysis, the greatest percentage improvement in UACR from baseline was observed in subjects who presented with the highest baseline UACR (801-3000 mg/g) and eGFR of at least 60 mL/min/1.73m². In this subset mean changes in UACR from baseline were +45 % in the placebo group (95% CI -6% to +121%, n=8), -23% in the CCX140-B 5 mg group (95% CI -55% to +32%, n=5; p = 0.03 vs control), and -39% in the CCX140-B 10 mg group (95% CI -61% to -7%; n=8; p = 0.004 vs control).

When taken together with results from the pre-clinical studies, and a favorable clinical safety profile (see Investigator's Brochure), these observations further support evaluation of CCX140-B in highly proteinuric renal diseases, including FSGS.

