9.3.8. Handling of Missing Data

For the MMRM analysis, data will be analyzed as is without missing data imputation. For ANCOVA analysis and analysis of responses, missing data will be imputed using the last observation carried forward (LOCF) method. This method may impute Week 12 missing data with the baseline value if there are no scheduled or unscheduled data prior to the missing time point. Other imputation method will be detailed in the SAP.

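### SAP sensitivity analysis 3 feeds carried-forward UPCR values to the MMRM as observed data; its bias has no dependable direction, and setting those visits to missing is a cheap improvement

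*SAP*

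**What the plan says.** Item 3 of the sensitivity analyses in SAP 3.4.1 opens: "A sensitivity analysis will be conducted using the same approach as the primary analysis". It makes one change for subjects identified as having taken a non-allowed medication: "all data after the initiation of the non-allowed medication will be imputed using the last observation prior to the initiation of the non-allowed medication". No multiple imputation or variance correction is described.

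The primary approach is an MMRM on the log ratio to baseline. Of that model the SAP says: "In the MMRM model, missing data will not be imputed. This analysis is unbiased under the missing at random (MAR) assumption". On the covariance it says "Toeplitz covariance matrix will be used to model within-subject variance-covariance structure for the model errors", with AR(1) and then compound symmetry as fall-backs. Protocol 9.3.8 takes the same line: "For the MMRM analysis, data will be analyzed as is without missing data imputation". It reserves LOCF for the ANCOVA and the response analyses. The SAP takes precedence over the protocol (SAP 1), but SAP 6 lists only the responder analysis and MCP-MOD as changes.

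Three other places bear on the point:

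- Item 1 of the same list averages two baseline values for this reason: "Given the high variability in morning void spot urine UPCR values".
- Protocol 5.5 keeps subjects who change medication on their scheduled visits, so UPCR after the start will usually have been measured.
- Protocol 2.4.1 reports that in the earlier diabetic nephropathy trial the fall in albuminuria was already visible at Day 15 and "reached a maximum decrease by the Day 85 visit".

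**The concern.** Item 3 discards measured values and lets one noisy spot UPCR stand in for several visits. In the double-blind period, a start soon after Week 1 means the Week 1 value fills Weeks 2, 4, 8 and 12. The model has no means of telling these copies from data.

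This can go wrong in two ways:

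- If the drug was started because UPCR was high, a partly chance high value is carried to Week 12 and the expected regression to the mean is lost. If this happens more often on placebo, the treatment effect looks too large.
- If the study-drug effect is still developing, the carried value freezes it at an early stage and the effect looks too small.

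Item 3 is the only analysis of the continuous primary endpoint in the full efficacy population that is aimed at non-allowed medication. Its purpose is to show whether the primary result depends on such drugs. An analysis whose own bias can run either way does that poorly, and with 10 subjects per arm each affected subject is 10% of an arm.

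**Working it through.** **1. The plan's own precision figure.** Inputs from Protocol 9.4 and SAP 2.2.4: SD 0.70, 10 per group, two-sided alpha 0.10. Half-width = t(0.95, 18 df) × 0.70 × √(2/10) = 1.734 × 0.70 × 0.447 = 0.543. For a ratio of 0.5, exp(ln 0.5 ± 0.543) = (0.29, 0.86). Both match the documents, with 0.70 read as the per-subject SD, as in Protocol 9.4.

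**2. Comparing the rule with the alternative.** Simulated trials: 500 per scenario, 4 arms of 10, visits at Weeks 1, 2, 4, 8 and 12, SD 0.70, true Week 12 ratio 0.5 for 15 mg against placebo. The model was a REML MMRM with Toeplitz covariance.

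Assumptions not in the documents:

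- 8% to 38% of an arm starts a non-allowed drug.
- Correlations at successive lags are 0.80, 0.72, 0.65 and 0.60.
- The effect is either building linearly to Week 12, with a placebo drift of 0.3, or flat from the first visit.
- Starts are unrelated to outcome (MCAR), driven by the last observed UPCR (MAR), or driven by the value that is then discarded (MNAR).

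Age was not modelled, and 36 df were used in place of Kenward-Roger.

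The table gives the shift in the Week 12 log difference from what it would have been had nobody started the drug. Positive means diluted. Monte Carlo SE is 0.005 to 0.008.

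| Starts | Effect | Carried forward | Set to missing |
|---|---|---|---|
| MCAR | building | +0.101 | -0.002 |
| MAR | building | +0.113 | -0.001 |
| MNAR | building | +0.176 | +0.071 |
| MCAR | flat | -0.003 | -0.002 |
| MAR | flat | -0.038 | +0.003 |
| MNAR | flat | +0.010 | +0.064 |

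**3. Size.** With a building effect, carry-forward multiplies the ratio by exp(0.101) = 1.11 to exp(0.176) = 1.19, so a true 0.50 reads as about 0.55 to 0.60. In the MAR flat case it reads as 0.5 × exp(-0.038) = 0.48. Against the planned half-width, 0.101/0.543 = 19%, 0.176/0.543 = 32% and 0.038/0.543 = 7%.

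**4. Which is better.** Set-to-missing is clearly better in the three building cases, slightly better in MAR flat, equal in MCAR flat and worse in MNAR flat.

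**5. Precision and coverage.** Set-to-missing raises the mean SE by 3% to 9%. Its 90% half-width is 0.545 to 0.579, against 0.530 with complete data. With the copies it is 0.522 to 0.547, close to the complete-data figure although real Week 12 data were thrown away. Coverage of the 90% interval is 88% to 92% with the copies and 92% to 93% with set-to-missing.

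**6. Upper limit on the cost.** If 2 of 10 per group gave no Week 12 information at all, the simple half-width would be t(0.95, 14 df) × 0.70 × √(2/8) = 1.761 × 0.70 × 0.5 = 0.616 instead of 0.543.

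**The case against.** Item 3 is one supplementary view, the primary analysis keeps the data as observed, and LOCF is a method the protocol names elsewhere. The per-protocol route covers some of the same ground. SAP 3.2.3 lists non-allowed medication among the grounds for exclusion and allows part of a subject's data to be dropped, and SAP 3.3.2 allows exclusion of visits. The responder analysis counts such subjects as failures. All this is true, but it does not replace item 3. The per-protocol set also removes subjects for low compliance and eligibility deviations, its visit-level exclusion is permissive and not specified for this event, and the non-responder rule serves only a binary endpoint.

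The evidence for a slowly building effect is thin. The earlier trial measured UACR in diabetic nephropathy, and a decrease was already present at Day 15. With a flat effect, the carry-forward shifts are small. This objection stands, and it is why the size must be given as a range.

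A reader might infer three stronger things, none of which is supported:

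- *Setting visits to missing removes the bias at no cost.* It does so only under MAR. A drug started for worsening proteinuria may not satisfy MAR, and in the MNAR flat case set-to-missing did worse than carry-forward. The interval also widens.
- *Item 3 cannot be interpreted.* Its interval coverage stayed close to nominal, and some of the shifts are small beside the half-width of 0.543.
- *The repeated values corrupt the Toeplitz estimate.* This is plausible, but it was not separately shown.

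**Conclusion.** The point holds as a minor improvement. Item 3 carries one value forward inside a model for which both documents otherwise reject imputation, and it overwrites data that will usually exist. It is not reliably conservative. Under the assumed start rates it diluted the Week 12 effect by about 0.10 to 0.18 on the log scale with a building effect, exaggerated it by about 0.04 in one case, and was near zero in two.

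Set-to-missing is the better default, being essentially unbiased under MCAR and MAR. Where starts depend on the discarded values, about 7% remains on the ratio (exp(0.064) to exp(0.071) = 1.07). These sizes rest on assumed start rates, start reasons, correlations and effect shapes. The direction of the bias in the actual trial cannot be read from the documents. The primary analysis is not affected.

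**What to change.** Reword item 3: for subjects identified before unblinding as having started a non-allowed medication, set UPCR values after the start to missing and run the primary MMRM unchanged. Add that the analysis targets the outcome had the drug not been started, that it relies on MAR, and that the number affected will be reported per arm. Keep the carried-forward version, if wanted, only as a secondary display. Ideally add one departure-from-MAR check, such as a delta-adjusted analysis, because MAR is the weak point here.

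The core change is one sentence in the SAP and little programming; the delta-adjusted check is extra work. The statistical cost is a standard error about 3% to 9% larger in the cases simulated. A subject who starts the drug before the first post-baseline visit drops out of the model, and some bias remains if starts depend on the values removed.
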